4.7 Packaging

Bruschettini Srl, Genoa, Italy will supply our investigational pharmacy with standard packaging bottles containing 120# of the 250 mg capsules (15 day supply).

4.8 Receiving, Storage, Dispensing and Return

4.8.1 Receipt of Drug Supplies

Bruschettini Srl, Genoa, Italy will be supply the drug in original packaging to our Investigational Pharmacy at Washington University who will distribute it.

4.8.2 Storage

Capsules are stored in a controlled environment at room temperature in the study pharmacy. Adherence will be made to the manufactures expiration date. No other special handling requirements during storage

4.8.3 Dispensing of Study Drug

Patients will receive a 6 week supply of the drug at initiation visit.

4.8.4 Study Drug discontinuation

All subjects who discontinue study drug should be considered withdrawn from the study and should complete the study completion visit assessments. If subjects fail to return for these visits, or are unable to do so, every effort will be made by the investigator to contact them or a knowledgeable informant by telephone or by

sending appropriate correspondence (i.e. certified letter) that will become part of the investigator's file to record that efforts were made to reach the subjects.

4.8.5 Subject Withdrawal Criteria

Subjects may voluntarily withdraw from or be withdrawn from the study at the discretion of the investigator (or sponsor) at any time. Patients may be withdrawn from the study if any of the following occur:

- 1. subject withdrew consent
- 2. Clinically significant new abnormal laboratory value that requires new therapy which may impact the study or suggests the patient is having an adverse response to TUDCA.
- 3. adverse event
- 4. clinically significant abnormal test procedure result
- 5. protocol violation
- 6. administration of prohibited concomitant medication

If such withdrawal occurs, subjects should complete the Study Completion visit assessments at the investigators' discretion. If subjects fail to return for these visits, or are unable to do so, every effort should be made by the investigator to contact them or a knowledgeable informant by telephone or by sending appropriate correspondence (i.e. certified letter) that will become part of the investigator's file to record that efforts were made to reach the subjects. If the subjects fail to return for visits, the investigator must determine the primary reason for a subject's premature withdrawal from the study, and record this information on the Study Completion CRF page.

4.8.6 Return or Destruction of Study Drug

At the completion of the study, there will be a final reconciliation of drug shipped, drug consumed, and drug remaining. This reconciliation will be logged on the drug reconciliation form, signed and dated. Any discrepancies noted will be investigated, resolved, and documented prior to return or destruction of unused study drug. Drug destroyed on site will be documented in the study files.

5 Study Procedures

Table 1 summarize study procedures, complementing Fig 1 above. Also see Appendix 1

	Visit	1	2	3	4	5	5
	Week #	≤ 2 weeks prior to baseline	0	2	4	6	8
vent		Screening	g Baseline	Week2	Week 4	Final visit - 6 weeks	Phone Ca follow up
Visit type	Clinic or Phone call based on clinic visit	х					
	Endoscopy		х			х	
	Phone Call			x	x		x
Coordinator Services	Informed consent	х					
	Inclusion/Exclusion Criteria	х					
	Demographics	х					
	Con Med review	х	х	х	х	х	
	Provide stool collection kit to patient	х					
	Stool Specimen Collection		х			х	
	Phlebotomy (Note LFT's will be drawn between week 2 to 4)		х	х		х	
	Lab Processing		х			х	
	Vital Signs		х			x	
	QoL Questionnaire (SIBDQ)		х	х	х	х	
	Medication Dispensing-CRC		х				
	Medication Accountability			х	х	х	
	Adverse Event Monitoring		х	x	х	x	x
	Telephone Call Assessment/Follow-up			x	x		x
Investigator Services	Partial Mayo Score Assessment			х	х		х
	Full Mayo Score with Endoscopic Score		х			х	
	Medical History for study	х					
Procedure	Sigmoidoscopy/Colonoscopy		х			х	

Endoscopic disease activity. The complete Mayo score will be completed at baseline and after 6 weeks of treatment, based on stool frequency, rectal bleeding, endoscopic findings and physician's global assessment³². In this trial, we are adapting the Mayo Scoring used in the OCTAVE clinical trial program.³³ Whereas standard Mayo scoring designates mild friability as an endoscopic subscore of 1, in the OCTAVE clinical trial program, any sign of friability led to an endoscopic subscore of 2. See Appendix 1.

Colonoscopic biopsies will be obtained under our current approved protocol (#201111078, DDRCC Biobank). Patients will be enrolled and consented by the Washington University site coordinators. Consent will be obtained in the outpatient clinic, the outpatient endoscopy suite or in the hospital with the permission of the treating physician. Up to 12 additional endoscopic biopsies will be obtained and used as a source for RNA, DNA or protein extraction, immunohistochemical analysis as described below.

Tissue Biopsy. Tissues will be obtained from inflamed and adjacent non-inflamed colon as available. The PI and Co-I's as well as clinical collaborators are highly skilled at colonoscopy with biopsy having performed thousands of these procedures. Moreover, investigators have routinely used colonoscopy for grading of endoscopic severity and tissue sampling for histology and study purposes. These procedures are generally tolerated well by patients.

Stool sample collection will be performed by protocol of the Washington University DDRCC Biobank Core https://ddrcc.wustl.edu/ with patient directed collection and courier- based delivery.

Geboes Histology Score: All biopsy specimens will be evaluated by the simplified Geboes Histology Score³⁴ based on the original Geboes Index.³⁵ This is provided in Appendix 1, Table 2.

Quality of Life Questionnaire: Health Related Quality of Life will be assessed by the Short Inflammatory Bowel Disease Questionnaire (SIBDQ) which has been validated in ulcerative colitis.^{36, 37} Measures quality of life as measured in four domains, bowel symptoms, emotional health, systemic systems and social function.

Additional Analysis on Samples and collection of samples for future studies. *Measurement of serum bile acid concentration*. Blood will be collected before and after TUDCA treatment, along with safety labs. Plasma bile acids will be measured using high-performance liquid chromatography tandem mass spectrometry.³⁸ These studies will be carried out in the metabolomics core at Washington University School of Medicine and overseen by [name]. We will measure total AND individual serum bile acids (including TUDCA). These measurements will be conducted on fasting serum obtained at the start of TUDCA and at timed intervals (at endoscopic evaluation and week 2).

Microbiota composition analysis. As indicated above, stool samples before and after TUDCA treatment will be collected for potential future analysis of microbiota. In the event that we proceed with metagenomic profiling (which would be based on the objective responses noted) microbial community composition will be determined by 16s metagenomic sequencing using the Illumina MiSeq platform. Libraries will be prepared in-house according to Illumina protocols and pooled libraries will be sent to the SBPMDI for deep sequencing. The resulting sequence data will be analyzed with the current version of Qiime ³⁹.

We recognize that TUDCA treatment may not have a significant impact on gut microbiota composition, as our preliminary data from IBD mouse models showed and for this reason will collect stool samples but not undertake metagenomic profiling at this time.

Future analyses. We will biobank tissues, stool and serum for deeper immunologic analyses that may be pursued with additional funding from alternative sources. This study will provide a rich resource for expanded immunological studies and will bank biospecimens (snap frozen, RNA later tissue, serum, stool) for future studies including full cytokine profiles and innate/adaptive immune readouts. These will be processed and stored in our NIDDK sponsored Digestive Diseases Research Center Biobank Core. Stool will also be stored for future microbial/metabolome analyses.

6 Statistical Plan and Outcome Analyses

ER stress and cell death markers. We expect that TUDCA treatment will reduce ER stress in colon biopsy tissues from subjects with symptomatic ulcerative colitis (UC), as judged by expression levels of ER stress markers as we have observed in IBD mouse models. Colon biopsy samples from inflamed and (if available) adjacent non-inflamed colon before and after 6 weeks of TUDCA treatment will be harvested for analysis listed below.

As the primary study endpoint, we will assess the change in ER stress markers, including eIF2 α phosphorylation, XBP1s and BIP/GRP78, in colon biopsy tissues before and after 6 weeks of TUDCA treatment.

BIP, XBP1 splicing, phosphorylated eIF2 α will be assessed by Western blot and RT-PCR and immunohistochemistry (IHC). Other ER stress markers, such as PERK, ATF4, CHOP, IRE1 α and ATF6 α will also be examined. In addition, we expect that cell death markers in colon biopsy tissues will also be downregulated, including cJUN, JNK, cleaved caspase 2 and cleaved caspase 3. We will also monitor expression of inflammatory cytokines, IL-1B, TNF α , IL-6 and IFN γ . Additional samples aliquots will be saved (flash frozen and RNAlater) for future studies evaluating adaptive and innate immune readouts.

[name], the co-PI of this study, has a broad background in ER stress and cell death, and discovered the therapeutic role of TUDCA in IBD mouse models with support from CCFA. His laboratory has extensive experience in evaluation of ER stress, inflammation and cell death markers by western-blotting, PCR and IHC in both mouse models and human samples. All the colon biopsy samples will be sent under dry ice for analysis by [name] laboratory. [name], a Research Associate in [name] laboratory will be responsible for analyzing and processing data from the clinical samples.

Significance of primary outcomes: Changes in ER stress markers will clarify the mechanisms through which TUDCA may act to alleviate inflammation in colon tissue of subjects with UC.

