Recent studies link ER stress to the pathogenesis of IBD. Patients with active Crohn's disease and ulcerative colitis exhibit signs of ER stress in their ileal and/or colonic epithelium⁷⁻⁹. In addition, human genetic studies of IBD have identified primary genetic abnormalities in several genes including *XBP1*, *AGR2*, and *ORMDL3* that encode proteins associated with ER stress^{1, 10-13}. Previous studies indicate that cells with a high load of protein folding and secretion are sensitive to altered ER homeostasis and this can induce inflammatory response gene expression^{1, 2, 5, 14, 15}. Intestinal microbiota and their molecules stimulate IECs to increase secretion of mucins and antimicrobial peptides that can overwhelm the protein secretory capacity of IECs. Conversely, exposure to inflammatory stimuli can cause ER stress¹⁵. Upon exposure to high levels of exogenous antigens and inflammatory cytokines in the intestinal lumen, IECs may require efficient UPR-mediated ER chaperone induction to survive the heavy burden of protein folding and secretion.

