1.5 Dose Rationale and Risk/Benefits

A weight based regimen for TUDCA will be used, administering it in 3 divided doses which corresponds to an average dose of 20-25 mg/kg/day accordingly using 1750 mg daily for patients <75 kg and 2000 mg daily for patients ≥75 kg.

It has been shown that TUDCA at the dose of 25mg/Kg/day can achieve maximum composition in the serum and bile in patients with primary biliary cirrhosis¹⁹. Previous clinical studies also have shown that 1 to 6 months of TUDCA treatment with 1750mg/day is efficacious and safe in patients with different diseases, including primary biliary cirrhosis^{19, 27, 28}, liver cirrhosis²⁹, HCV-related chronic hepatitis³⁰ and insulin resistance¹⁷. Animal studies also suggest that TUDCA appears to be very well tolerated even at high doses.

Patients will not be charged for the drug. This will be supplied in original packaging by Bruschettini Srl, Genoa, Italy. TUDCA distribution will be carried out by our Investigational Pharmacy at Washington University. Patients will receive a 6 week supply at initiation visit.

2 Study Objectives

Intestine biopsy samples from inflamed and adjacent non-inflamed intestine tissues before and after the TUDCA treatment will be harvested to evaluate ER stress status by western-blotting for ER stress induced proteins, qRT-PCR and immunochemistry staining. The disease severity will be measured by the Geboes histology index and the complete Mayo score before and after the TUDCA treatment will be monitored. The **overall goal** of this project is to determine if the research findings in mouse IBD models can be successfully translated to humans and thereby provide an adjunctive to optimize therapeutic options in IBD patients focused on the epithelium and with a desirable safety profile. To address this, we propose the following **Specific Aims**:

SA 1. Determine the effect of TUDCA treatment on ER stress in colon biopsy tissues from subjects with symptomatic ulcerative colitis as a primary endpoint.

We expect that TUDCA treatment will reduce ER stress in colon biopsy tissues from subjects with symptomatic ulcerative colitis (UC), as judged by expression levels of ER stress markers. As a primary study endpoint, we will assess:

A. The primary endpoint will be the change in ER stress markers, including eIF2α phosphorylation, XBP1s and BIP/GRP78, in colon biopsy tissues before and after 6 weeks of TUDCA treatment.

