2.2 Primary Study Endpoints

As the primary study endpoint, we will assess the change in ER stress markers, including $eIF2\alpha$ phosphorylation, XBP1s and BIP/GRP78, in colon biopsy tissues before and after 6 weeks of TUDCA treatment.

BIP, XBP1 splicing, phosphorylated eIF2 α will be assessed by Western blot and RT-PCR and immunohistochemistry (IHC). Other ER stress markers, such as PERK, ATF4, CHOP, IRE1 α and ATF6 α will also be examined. In addition, we expect that cell death markers in colon biopsy tissues will also be downregulated, including cJUN, JNK, cleaved caspase 2 and cleaved caspase 3. We will also monitor expression of inflammatory cytokines, IL-1B, TNF α , IL-6 and IFN γ . Additional samples aliquots will be saved (flash frozen and RNAlater) for future studies evaluating adaptive and innate immune readouts.

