3.1 Inclusion Criteria

- 1) Ages Eligible for Study: 18 Years to 65 Years;
- 2) Confirmed ulcerative colitis disease through radiographic, endoscopic and/or histologic criteria;
- 3) Confirmed with active ulcerative colitis (defined as a complete Mayo score \geq 5 with endoscopic subscore of \geq 1) See Appendix for Mayo Score using recent adaptation to include any friability on endoscopy to be scored as "2".
- 4) On a stable dose of medications for IBD (i.e. no change in medication within 4 weeks of study enrollment) and not planning to initiate new medication other than TUDCA.

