6.1 Sample Size Determination for Primary Endpoint

Estimates of change in the primary outcomes: We expect that TUDCA treatment will lead to similar changes on ER stress markers in UC patients as that in IBD mouse models. As judged by quantification results of western blot, the expression levels of ER stress markers in IBD mouse models were significantly reduced by 25% to 45% after TUDCA treatment.⁴ A previous publication, as well as our own data, has shown that standard deviations of the ER stress markers are less than ½ of the means in intestinal biopsy samples of IBD patients⁴⁰. Considering there might be greater variation after the TUDCA treatment, we set the standard deviations at half of the means of all the ER stress markers (Table 2).

Table 2 Sample size calculation

ER stress markers	Difference between means	Estimated standard deviation	Sample size at power=0.8	Sample size at power=0.9
p-elF2α	1.16-0.64=0.52	0.26	5.09	6.39
XBP1s	1.21-0.73=0.48	0.24	5.09	6.39
BIP	1.13-0.84=0.30	0.15	5.09	6.39

Power Estimates for each primary endpoint: We used the quantification results of western blot on ER stress markers to calculate the sample size needed. Since the impact of TUDCA on intestine tissues in humans has not been examined, we used the difference between the mean values of ER stress markers in groups treated with or without TUDCA that we obtained in murine studies.⁴ Power analysis using the R software shows that 7 patients are sufficient to detect the difference before and after the treatment, when P<0.05 is considered significant. Due to the relatively variability in IBD patient disease activity and high dropout rate in IBD clinical trials, we will enroll a total of 12 patients will be recruited for the study with an expected

Statistical analysis: We will be specifically interested in the statistical contrasts that compare before and after TUDCA treatment. Correlation between the primary end point and secondary end point will also be examined. The appropriateness of all analysis of variance and covariance models will be evaluated using regression residuals. If normality or homoscedasticity requirements are violated, data transformations will be explored and, if appropriate transformations cannot be found, analyses may be done semi-parametrically using the ranks of the data.

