We anticipate that TUDCA therapy will reduce ER stress and promote mucosal healing. As TUDCA has the potential to increase stool frequency, it is important to measure efficacy through objective measures (endoscopy and histology) as well as clinical symptoms. Thus, we will obtain a complete Mayo UC score at weeks 0 and 6 and a partial (no endoscopic subscore) at weeks 2 and 4.32 Biopsies will be obtained at both

endoscopic procedures and objectively scored by the Goebes index. Thus, secondary endpoints will include the following using FDA recommended UC Clinical trial guidelines⁴¹:

- 1) Mucosal Healing: A decrease of at least 1 point on the Mayo endoscopic subscore with a final score of 0 or 1 will be used as a marker of mucosal healing.
- 2) Clinical Response: A decrease in Mayo Score of ≥ 3 points and a decrease in Mayo Score of ≥ 30% from baseline and a decrease in the rectal bleeding score of ≥ 1 or an absolute rectal bleeding score of 0-1.
 - a. Clinical Remission will also be recorded if achieved as defined by a total Mayo Score of ≤2 with no subscore >1 and improvement of endoscopic appearance of the mucosa (Mayo 0 or 1).
- **3) Histologic activity:** *Histologic disease activity.* Colon biopsy samples will be harvested and fixed as described. H&E stained sections will be evaluated for tissue damage and inflammation by a gastrointestinal pathologist in a double-blinded manner, using the simplified Geboes histology index^{34, 35}

We expect that TUDCA treatment will significantly alleviate inflammation in colon tissues, which will be correlated with increased plasma concentration of TUDCA or the deconjugated form UDCA. We will collect stool samples both before and after TUDCA treatment for potential (longer range) studies of gut microbiota composition.

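### The before and after biopsies are defined by tissue state rather than location, and the primary endpoint does not say which tissue forms the pair

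*Combined protocol and SAP*

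**What the plan says.** Three places describe the tissue:

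- Section 2 (Study Objectives): "Intestine biopsy samples from inflamed and adjacent non-inflamed intestine tissues before and after the TUDCA treatment will be harvested". There is no qualifier.
- Section 5 (Study Procedures, Tissue Biopsy): "Tissues will be obtained from inflamed and adjacent non-inflamed colon as available". The qualifier may cover both tissue types or only the second.
- Section 6 (opening paragraph): "Colon biopsy samples from inflamed and (if available) adjacent non-inflamed colon before and after 6 weeks of TUDCA treatment will be harvested". The qualifier is attached only to the non-inflamed tissue.

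The primary endpoint (Sections 2, 2.2 and 6) is the change in p-eIF2α, XBP1s and BIP "in colon biopsy tissues before and after 6 weeks of TUDCA treatment". On the analysis, Section 6.1 says: "We will be specifically interested in the statistical contrasts that compare before and after TUDCA treatment".

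Three other parts of the plan bear on this. Section 1.1 links tissue state to the marker: "Conversely, exposure to inflammatory stimuli can cause ER stress". Section 6.2 anticipates mucosal healing, defined as "A decrease of at least 1 point on the Mayo endoscopic subscore with a final score of 0 or 1", but also warns that healing may need longer than the 6 weeks of treatment. Section 3.1 admits patients with an endoscopic subscore of 1.

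**The concern.** A before/after contrast needs both halves of the pair to be chosen by a rule that the treatment cannot influence. Here both halves are described by whether the tissue is inflamed. At week 6 that is itself an outcome, and one the plan hopes to change. Because the plan regards inflammation as a cause of ER stress, choosing tissue by its inflammation also tends to choose its marker level.

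The study has one arm and is open label. No control group would show the same sampling shift and cancel it, and nothing blinds the endoscopist who picks the site. At stake is whether a change in the primary markers can be read as a change in the tissue rather than as a change in where the biopsy was taken.

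**Working it through.** **1. What the passages fix.** Set side by side, Sections 2, 5 and 6 fix the time points and the tissue states. None of them, nor Sections 2.2 and 6.1, gives a segment or distance, a requirement to return to the baseline site, the tissue type that forms the primary pair, or a rule for a patient with no inflamed tissue at week 6. Section 6 makes only the non-inflamed sample conditional, so it takes inflamed tissue at week 6 for granted.

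**2. Direction of the bias.** Take the sites inflamed at baseline. Let *p* be the share that look healed at week 6, *D_h* the mean marker fall at those sites and *D_s* the mean fall at sites still inflamed. If markers follow inflammation, *D_h* > *D_s*.

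- Same-location pairs: mean fall = *p·D_h* + (1 − *p*)·*D_s*.
- Still-inflamed tissue only: mean fall = *D_s*. The shortfall is *p·(D_h − D_s)*, a bias against TUDCA.
- A switch to a never-inflamed site in a share *h* of patients: with no drug effect and a baseline gap *g* between the two kinds of site, the apparent mean fall is *h·g*, a bias towards TUDCA.
- No visible inflammation left: the inflamed pair is undefined, and the analyst must choose after the fact.

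The plan supplies none of *p*, *h*, *g*, *D_h* or *D_s*.

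**3. The plan's own figure.** Table 2 has a difference/SD of 0.52/0.26 = 0.48/0.24 = 0.30/0.15 = 2.0. A two-sample t-test at two-sided 0.05 with that ratio gives 5.09 per group (power 0.8) and 6.39 (power 0.9). This matches the table and rounds up to the stated 7. The calculation contains no term for tissue mix. Enrolment of 12 leaves room for 12 − 7 = 5 unusable pairs (5/12 = 41.7%) from all causes.

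Suppose, as an assumption, that undefined pairs were treated as missing, with dropout *d* and share undefined *u*. Usable pairs = 12(1 − *d*)(1 − *u*):

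- *d* = 0, *u* = 30%: 12 × 1.0 × 0.7 = 8.4
- *d* = 20%, *u* = 20%: 12 × 0.8 × 0.8 = 7.7
- *d* = 20%, *u* = 30%: 12 × 0.8 × 0.7 = 6.7
- *d* = 30%, *u* = 20%: 12 × 0.7 × 0.8 = 6.7

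If the ratio of 2.0 is read as a paired effect, power is still 0.99 at 7 pairs and 0.91 at 5. On the plan's own inputs, then, the number lost matters less than the fact that losses would fall on the best responders.

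**4. Illustration of the site switch.** Assume no drug effect, 12 paired differences with SD 1, a share *h* of week-6 samples taken from a never-inflamed site lower by *g* SD of the paired difference, and a t-test at two-sided 0.05. The simulated chance of a significant decrease (50,000 trials per case) is:

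| *h* | *g* = 1 | *g* = 2 |
|---|---|---|
| 0 | 0.025 | 0.024 |
| 20% | 0.08 | 0.14 |
| 30% | 0.13 | 0.27 |
| 50% | 0.29 | 0.60 |

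The apparent mean fall at *h* = 30% is 0.3 × 1 = 0.3 SD or 0.3 × 2 = 0.6 SD. These figures apply only if the site changes. They show that the primary test is sensitive to the gap in the plan, not how large the bias will be.

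**The case against.** The other side has a good deal right.

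- **The text is silent; it does not order a switch.** Nothing says that the site is re-chosen by appearance at week 6, and an experienced endoscopist may well return to the baseline site. This stands, but good practice that is not written down does not protect the primary contrast.
- **Healed does not mean free of inflammation.** A reader might infer that every patient who heals lacks an inflamed week-6 sample. The documents do not support that: healing includes a final subscore of 1, which counts as active disease at entry. The problem is confined to patients with no visible inflammation left. Section 6.2 itself doubts that 6 weeks is enough, which may make them few.
- **The pair is not necessarily lost.** Section 6.2 takes biopsies at both endoscopies, the endpoint is not limited to inflamed tissue, and no passage excludes a healed patient.
- **A percentage bias cannot be read off.** A reader might multiply a guessed share healed by a guessed tissue difference, for example 3/12 × 20% to 40% = 5% to 10%. Those inputs are not in the documents. A pair from one site that was inflamed and then healed would show the same fall, and that may be the drug effect.
- **Reach is not shown to be a problem.** Table 1 lists the same sigmoidoscopy/colonoscopy option at both visits.
- **Histology is graded.** All specimens get a simplified Geboes score, read blind. This helps interpretation, but no adjustment is prespecified and a score cannot recover a site that was not sampled.
- **A rule may exist elsewhere.** Biopsies are taken under a separate biobank protocol. That document, Figure 1 and Appendix 1 were not available. This stands and lowers confidence.

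**Conclusion.** The point holds as a gap in the sampling rule and in the definition of the primary pair. In the text available, week-6 tissue is described by a post-treatment state and the pair is not named. The primary contrast can therefore be biased in either direction, and a patient with no visible inflammation has no defined pair.

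The size is unknown. The simulated rise in false positives rests on assumed switch rates and gaps, and on the week-6 sample coming from a different, never-inflamed site. A same-site pair that goes from inflamed to healed is not a flaw and should not be counted as one. Confidence is medium, pending sight of the biobank protocol, Figure 1 and Appendix 1. The matter should be settled before sampling starts, because a site missed at week 6 cannot be recovered in the analysis.

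**What to change.** In Section 5:

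- At baseline, record the segment and distance of the inflamed biopsy, at a site that the week-6 procedure will reach.
- At week 6, re-biopsy that location whatever it looks like, and record its appearance.

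In Section 6:

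- Define the primary contrast as the same-location pair from tissue inflamed at baseline.
- Analyse adjacent non-inflamed pairs separately as secondary, without pooling the two.

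If the biobank protocol already holds a site rule, cite it and still name the primary pair in Section 6.

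The cost is one more line on the endoscopy form and a sentence in each of the two sections. Re-location of the site will be slightly imperfect, which adds some noise. No extra biopsies are needed, since Section 5 already allows up to 12.

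### Three primary markers have no stated success rule, and Table 2 uses half the differences as SDs where the text says half the means, so seven patients is not supported

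*Combined protocol and SAP*

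**What the plan says.** Section 6 states: "As the primary study endpoint, we will assess the change in ER stress markers". Sections 2 and 2.2 define the primary endpoint in the same way, and all three places list p-eIF2α, XBP1s and BIP/GRP78 as included. The direction is predicted: "We expect that TUDCA treatment will reduce ER stress in colon biopsy tissues from subjects with symptomatic ulcerative colitis".

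Section 6.1 treats the markers one at a time: "Power Estimates for each primary endpoint: We used the quantification results of western blot on ER stress markers to calculate the sample size needed". It concludes that "7 patients are sufficient to detect the difference before and after the treatment, when P<0.05 is considered significant", and then enrols 12, citing variable disease activity and the "high dropout rate in IBD clinical trials". On variability it says "we set the standard deviations at half of the means of all the ER stress markers".

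Section 6 measures the markers by Western blot, RT-PCR and immunohistochemistry, in inflamed and, where available, adjacent non-inflamed colon. The use of Western blot for sizing and the order in which the tissues are listed suggest a default, but nothing is labelled supportive. The statistical analysis paragraph covers before/after contrasts, model checks, transformations and ranks. It gives no lead marker, composite, success rule or division of alpha.

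**The concern.** Two gaps affect how the primary result will be read.

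First, the plan has a primary endpoint, a power calculation, a significance threshold and a predicted direction, but it does not say which pattern of results would confirm the prediction. One significant reduction out of three could be presented as success or as failure, and the choice could be made after the data are seen.

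Second, the sample size statement depends on an effect of two standard deviations for every marker. That ratio is a product of how the SD column was filled in: each SD is half of its own difference, so each ratio is 2 whatever the marker. If the SD is what the text says it is, the assurance attached to seven patients is lost, and the claim for 12 weakens unevenly across markers.

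**Working it through.** **1. Reproduce Table 2.** Inputs: differences 0.52, 0.48 and 0.30; SDs 0.26, 0.24 and 0.15. Each ratio is 2.0 (0.52/0.26, 0.48/0.24, 0.30/0.15). A two-sample t test at two-sided 0.05 with effect size 2, by noncentral t, gives 5.09 per group at 80% power and 6.39 at 90%, an exact match. Other variants do not match: two-sample one-sided 3.99 and 5.13; paired two-sided 4.22 and 4.91; paired one-sided 3.34 and 3.93. So P<0.05 is two-sided, which leaves 2.5% in the direction of a reduction, and the seven is 6.39 rounded up.

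**2. False success under each reading, with no true effect on any marker.**
- One named marker: 2.5%.
- Any one of three, independent: 1 − 0.975³ = 7.3%.
- Any one of three, correlated (simulated paired t tests, n=7 and n=12): about 6.9% at correlation 0.3, 6.5% at 0.5 and 4.4% at 0.9.
- All three required: 0% to about 1% for correlations 0 to 0.9.

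The documents give no correlation between markers, so these values are assumptions.

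**3. Compare the SD text with Table 2.**

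| Marker | Means | Half baseline mean | Half week-6 mean | Half difference | Table 2 SD |
|---|---|---|---|---|---|
| p-eIF2α | 1.16, 0.64 | 0.58 | 0.32 | 0.26 | 0.26 |
| XBP1s | 1.21, 0.73 | 0.605 | 0.365 | 0.24 | 0.24 |
| BIP | 1.13, 0.84 | 0.565 | 0.42 | 0.145 | 0.15 |

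The means are the untreated and treated mouse values, used here as baseline and week 6. Neither mean, nor their average, halves to the tabulated SD; the difference does. (1.13 − 0.84 is 0.29; the table prints 0.30.) As a share of the baseline mean the tabulated SDs are 0.26/1.16 = 22%, 0.24/1.21 = 20% and 0.15/1.13 = 13%, not 50%.

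**4. Power with the SD the text sets.** Paired t test, two-sided 0.05, within-patient correlation r. The SD of the change is √(s₁² + s₂² − 2r·s₁·s₂); the noncentrality is √n × difference / SD of change.

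- *Half the baseline mean at both visits, r = 0.5.* The SD of change equals s₁. Effect sizes: 0.52/0.58 = 0.897; 0.48/0.605 = 0.793; 0.29/0.565 = 0.513.
- *Half of each visit's own mean, r = 0.5.* The SD of change is 0.503, 0.528 and 0.508. Effect sizes: 1.033, 0.910 and 0.571.

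| Power (p-eIF2α, XBP1s, BIP) | n=7 | n=12 |
|---|---|---|
| Half baseline mean | 51%, 42%, 21% | 81%, 71%, 37% |
| Half own mean | 63%, 52%, 25% | 90%, 82%, 44% |

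Sensitivity to r, baseline-mean SD, r from 0.3 to 0.7: at n=7, 39-72%, 32-62% and 16-32%; at n=12, 67-95%, 56-90% and 28-55%. With the own-mean SD at r = 0.7, p-eIF2α at n=7 reaches 77%.

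**5. Is the two-sample formula the problem?** No. With Table 2's own SDs, a paired test at n=7 has 87% power at r = 0 and 99% at r = 0.5. The SD drives the result.

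**The case against.** The strongest reply is that this is a 12-patient, single-arm, open-label Phase I study whose marker readout is meant to explain mechanism: "Changes in ER stress markers will clarify the mechanisms through which TUDCA may act to alleviate inflammation". Formal familywise control is optional there, and powering each marker separately fits marker-by-marker reporting, in which each test carries its own 2.5%. This stands as an argument on severity. It does not supply the missing sentence on how the three results are to be read together.

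A reader might infer that the trial runs at a 4-7% false-success rate. The documents do not support that. The figure applies only under an any-one rule, which the plan neither adopts nor excludes; under an all-three rule no adjustment is needed. What is shown is ambiguity, not inflated error.

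On the SD, the plan reports observed values below half of the means, so the true SD could be smaller and power higher. That is fair, but the plan then deliberately chose half of the means as its planning value, and Table 2 does not use it. Nor should seven completers be read as a dropout forecast: the sentence on expected numbers breaks off in the available text. Seven is used because it is the plan's own figure.

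A reader might also infer bias from the biopsy site, because the visible text does not tie the week-6 segment to the baseline segment. That is not established. Biopsies are taken under a separate biobank protocol which, like Figure 1 and Appendix 1, was not available and may settle it. It is at most a separate query.

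**Conclusion.** The point holds at low severity, in two parts.

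The three primary markers have no decision rule. Depending on the rule chosen later, the chance of a false success runs from about 0-1% (all three) through 2.5% (one named marker) to 4.4-7.3% (any one, at assumed correlations from 0.9 to 0).

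The statement that seven patients suffice does not follow from the SD the plan says it uses. At n=7 no marker reaches 80% power under either reading of half the means, for assumed within-patient correlations from 0.3 to 0.7. At n=12 with correlation 0.5, p-eIF2α is adequate, XBP1s is borderline (71% or 82%) and BIP is weak (37% or 44%), before any adjustment and with no dropout. The power figures also rest on the plan's mouse differences carrying over to patients.

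None of this affects dosing or stopping, and it does not show that the study needs more patients. It affects what the primary result can be said to show.

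**What to change.** 1. In Section 6.1, reconcile the SD text with Table 2. Then restate the power and the seven-patient statement for a paired analysis, giving the assumed within-patient correlation. Keep the enrolment of 12.
2. In Section 6, define the primary analysis as the within-patient change in Western-blot p-eIF2α, XBP1s and BIP in inflamed tissue. Test the three with Holm at overall two-sided 0.05, claim only markers that pass, and report all three estimates with confidence intervals. Label the other assays, non-inflamed tissue and other markers supportive.

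Other pre-specified rules would also close the gap. A single lead marker keeps the full alpha for that marker. An all-three rule needs no adjustment, but its power cannot exceed that of BIP (37% or 44% at n=12). Holm avoids both the choice of a lead marker and that ceiling.

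The cost is wording plus some power per marker. With the baseline-mean SD, correlation 0.5 and n=12, the Bonferroni floor (0.0167 per test) lowers 81%, 71% and 37% to 62%, 50% and 20%. Holm recovers part of this: about 64-67%, 55-57% and 30-35% for marker correlations of 0.3 to 0.9. With seven completers the floor is 29%, 22% and 9%. Under Table 2's SDs and its two-sample method the loss is smaller: 93% to 81% at n=7 and 99.7% to 98.5% at n=12. This is why the SD must be settled first.

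Separately, check whether the biobank protocol already fixes the week-6 biopsy segment.
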